10.0 PHARMACOKINETIC STUDIES

Busulfan will be infused with a fresh infusion set whenever pharmacokinetic assessments will be performed. The tubing will be primed with the busulfan, and the entire volume plus a volume of normal saline flush equal to the priming volume will be infused at a constant rate into a central venous catheter over the 3-hour infusion time. Sampling will be done with the test dose, and with the first and fourth treatment doses. If, for logistical reasons, sampling on day 4 is not possible, then day 3 may be used as the time point for the second sample. Samples will be taken from a peripheral vein (through the same line after additional flushing) into prechilled heparin tubes with plasma separation within 30 minutes.

The actual start and stop times of busulfan will be recorded, as will the exact times when the blood levels are drawn. Plasma will be separated by centrifugation at 2500 rpm for 10 minutes at 4°C within 1 hour, placed in cryogenic vials, and analyzed or stored at -40°C until analyzed by a validated high-pressure chromatography in the Pharmacokinetics core lab at the University of Chicago Cancer Center.

10.1 *Timing of samples:*

10.1.1 *Test dose:*

Blood samples (5 mL) will be taken before Bu infusion, at 175 minutes (five minutes before completion), 240 minutes (1 hour after completion) 300 minutes (2 hours after completion), 360 minutes (3 hours after completion) and 420 minutes (4 hours after completion) of the test dose

10.1.2 *Treatment doses 1 and 3 (or 4):*

Blood samples (5 mL) will be taken before Bu infusion, at 175 minutes (five minutes before completion), 240 minutes (1 hour after completion) 300 minutes (2 hours after completion), 360 minutes (3 hours after completion of the treatment dose 1 (day -6) and treatment dose 4 (day -3) (or in selected patients, treatment dose 3, day -2)

The Software program WinNonLin Pro ® will be used for calculating AUC.

11.0 PRETREATMENT EVALUATION

11.1 RECOMMENDED EVALUATION OF THE PATIENT

The pre-transplant evaluation of the patient will follow recommendations as per transplant policies (on website). The following list can be used for guidance.

- Complete history and physical examination
- Bone marrow biopsy and aspirate with leukemia markers,
- cytogenetics
- CBC, platelets, differential, reticulocyte count, PT and PTT
- Chest X-ray and PFTs with DLCO
- Baseline EKG,
- MUGA with measurement of LVEF
- Chemistry profile with complete liver function panel.
- Complete urinalysis
- HLA Class I and class II (molecular typing in case of unrelated donor transplantation)
- ABO and Rh typing
- Serum titers for CMV, HSV, HIV antibody, hepatitis screen and any other assays required for donor work-up by transplant unit policy (usually based on FDA recommendations and/or recommendations from federation for accreditation of cell therapy, FACT)
- Peripheral blood for chimerism studies.
- Lumbar puncture for cell count, protein, glucose, and cytology in patients with ALL and high grade NHL, or if prior history of CNS involvement.
- CT scan of the chest (with IV contrast) for all patients.
- CT of abdomen and pelvis for lymphoma/Hodgkin's disease patients only.
- Quantitative immunoglobulin, and bone survey for multiple myeloma patients only.
- Urine pregnancy test if female
- Any additional tests that may be required for clinical care and described in the BMT unit policies.
- 20 cc of blood and 5 cc of bone marrow will be stored on all recipients to be used for research purposes. **(including pharmacogenomic assays)**

11.2 RECOMMENDED EVALUATION OF THE DONOR

The pre-transplant evaluation of the donor will follow recommendations as per transplant policies (on website). The following list can be used for guidance.

- Complete History and Physical Examination
- CBC, platelets, differential, reticulocyte count, PT and PTT
- Chest X-ray
- EKG
- Electrolytes, BUN, Creatinine, SMAC, magnesium
- Complete Urinalysis
- HLA Class I and Class II typing (molecular typing in case of unrelated donor transplantation)
- ABO and Rhesus typing
- Serum titers for CMV, HSV, EBV
- HIV serology, Hepatitis screen and any other assays required for donor work-up by transplant unit policy (usually based on FDA recommendations and/or recommendations from federation for accreditation of cell therapy, FACT)
- Peripheral blood for chimerism studies.
- 20 cc of blood will be stored on all donors to be used for research purposes.
- 20 cc of blood will also be stored on each day of stem cell collection

12.0 EVALUATION DURING STUDY

12.1.1 EVALUATION DURING THE FIRST 100 DAYS

Evaluation during the first 100 days will be done as per routine for the allogeneic transplant patient (see transplant policies).

Restaging of disease and engraftment studies will be performed between day 25 and day 35.

12.1.2 DAY 100 EVALUATION (to be completed day 84-100)

The day 100 evaluation of the patient will follow recommendations as per transplant policies (on website). The following list can be used for guidance.

- 12.1.2.1 Review of Systems and Physical examination
- 12.1.2.2 CBC, differential, platelets, electrolytes, BUN, Creatinine, Magnesium, glucose, SMAC,
- 12.1.2.3 Bone marrow biopsy and aspirate with cytogenetics
- 12.1.2.4 Peripheral blood chimerism studies.
- 12.1.2.5 Bone marrow aspirate and biopsy
- 12.1.2.6 restaging of disease as indicated by disease specific testing.

12.1.3 EVALUATION DAYS 100-365 (patient without chronic GVHD)

The one year evaluation of the patient will follow recommendations as per transplant policies (on website). The following list can be used for guidance.

- 12.1.3.1 PE and screening labs at least monthly through day 365
- 12.1.3.2 Restaging of disease approximately 3 months, 6 months, 9 months and one year after BMT.
- 12.1.3.3 Follow-up for patients with chronic GVHD as per the chronic GVHD protocol.

12.1.4 ANNUAL EVALUATION

The yearly evaluation of the donor will follow recommendations as per transplant policies (on website) . The following list can be used for guidance.

- 12.1.4.1 Review of systems and physical examination
- 12.1.4.2 Schirmer's test
- 12.1.4.3 Chest X-ray
- 12.1.4.4 Pulmonary function tests
- 12.1.4.5 CBC, differential, platelets, electrolytes, BUN, Creatinine, glucose, SMAC, magnesium.
- 12.1.4.6 Bone marrow biopsy and aspirate with cytogenetics and chimerism studies.
- 12.1.4.7 Thyroid function tests
- 12.1.4.8 Restaging of leukemia by bone marrow aspirate and biopsy with cytogenetics and chimerism studies.
- 12.1.4.9 restaging of disease.

12.1.5 blood and bone marrow samples

Samples of blood and/or bone marrow will be obtained at the following time points:

- Prior to admission (BM and blood)
- On day 0 (Blood)
- On day 7 (Blood)
- On day 14 (Blood)
- On day 28 (BM and blood)
- Day 50 (Blood)
- Day 75 (Blood)
- Day 100 (Blood)
- Day 150 (BM and blood)
- At relapse (BM and blood)
- One year and yearly thereafter (BM and blood).

These samples will be stored for our ongoing studies of MRD and for assessment of immune reconstitution as well as chimerism. Chimerism will be determined by molecular analysis of peripheral blood samples.

An initial blood sample will also be stored for pharmacogenomic studies.

As of February 2013, after IRB approval, cryopreserved pre-transplant and post-transplant recipient specimens and pre-transplant donor specimens collected under this protocol will be used to evaluate the effects of minor histocompatibility antigens and major histocompatibility antigens (HLA) mismatches on transplant outcomes. Genomic, proteomic, functional tests, and other tests will be performed to identify predictors of compatibility between patient and donors. These predictors may help future studies exploring identification of the most suitable donor(s) for patients planning allogeneic hematopoietic cell transplantation. This will be done for protocol IRB 11300A and IRB 12-0132.

DNA isolation will be performed from 1 ml of EDTA-blood sample from each patient sample using the Magnapure Compact system for DNA isolation (Roche Applied Science).

Sample shipment information

3-5 ml of patient blood sample should be drawn in a purple top EDTA tube. Samples should NOT be spun down. Samples should be shipped in appropriate packaging by overnight delivery at room temperature. If a sample cannot be sent the day it is drawn, it can be stored refrigerated at 4°C for 2-3 days prior to shipment. Samples may be shipped to the laboratory on Monday through Thursday. Samples should not be shipped on Friday as the laboratory cannot receive samples on the weekend. All samples need to be appropriately labeled with patient name/ID and protocol number. In addition, all samples should be accompanied by paperwork that specifies the sample ID, protocol number, physician's name and contact information (address, phone number and fax number) to whom the result needs to be reported to. Samples should be shipped to the University of Chicago Genetic Services Laboratory at the following address:

University of Chicago Genetic Services Laboratory
Department of Human Genetics
The University of Chicago
[name]
[name]
[name]

[contact]
[contact]

Protection of confidentiality

Patient samples will be processed and genotyped at the University of Chicago Genetic Services Laboratory which is a CAP and CLIA certified laboratory that routinely performs genetic testing of multiple disorders on a clinical basis. The laboratory

therefore has all necessary procedures related to protecting of patient confidentiality. All samples will be processed by trained technologists and results reported only to the patient's physician or other appropriate health care person. All patient samples will have a protected identification code that will be used.

Table I: Schedule of tests (The following table can be used for guidance. Some individualization may be necessary)

Tests & Observations	Prior to Study	During conditioning	Day of Transplant	Day 28 (± 1 wk) Post Transplant	Day 100, (± 1 wk)	Day 180 (± 1 wk)	Post-Tx Follow-up**
History and Progress Notes	X		X	X	XX		X
Physical Examination	X	X	X	X	XX		X
Pulse, Blood Pressure	X					X	X
Height/Weight X		X				X	X
Performance Status	X		X	X	XX		X
Toxicity Assessment			X	X			
AGVHD Assessment			X	X	XX		
CGVHD Assessment					X		
Lumbar puncture	E						X
Surveillance Tests							
EKG	X						
PFTs	X						X
Thyroid function tests							X
Schirmer test							X
MUGA (or 2-D Echo)	X						
Staging							
Chest x-ray, PA & Lateral	X						X
CT/MRI scan chest/abd/pelvis	X				D		D
Bone Marrow Asp & Bx	X			X	XX		X
Laboratory Studies							
CBC, Differential, Platelets	X	X	X	X	XX		X
Serum Creatinine, BUN	X			X	XX		X
Serum Electrolytes	X			X	XX		X
AST, ALT, Bilirubin	X			X	XX		X
LDH	X			X	X		X
Urinalysis	X						
serum or u-HCG (for pre-menopausal females)	X						
Hepatitis Screen, CMV Ab, HIV, EBV, HSV-I	X						
Serologies & HLA Typing	X						
Pharmacokinetics							
Chimerism							
Peripheral blood (20 cc min.)*	X		X	X	XX		X
Donor peripheral blood (5 cc)	X						
Immune reconstitution							

Tests & Observations	Prior to Study	During conditioning	Day of Transplant	Day 28 (± 1 wk) Post Transplant	Day 100, (± 1 wk)	Day 180 (± 1 wk)	Post-Tx Follow-up**
Peripheral blood (20 cc min.)	X		X	X	XX		X
Optional Tests (i.e. dependent on patient approval)							
MRD (WT1 or IgG gene)							
Peripheral blood (20 cc min.)	X		X	X***	XX		X
Bone marrow aspirate (8 cc)	X			X	XX		X
Pharmacogenomics	X						
Blood (20 cc)	X						
Bone Marrow (5 cc)	X						

** At one-year post-transplant, and then yearly thereafter for a maximum of 5 years from study entry, and at relapse.

*** Additional samples on day 7, 14.

D For lymphoma patients. Other tests may be indicated in myeloma (e.g MRI or bone scan)

E: Only for pts with ALL, High grade lymphoma or history of CNS involvement.

Failure to engraft will be defined as lack of evidence of hematopoietic recovery (ANC $<500/\text{mm}^3$ and platelet count $<20,000/\text{mm}^3$) by day +35, confirmed by a biopsy revealing a marrow cellularity $<5\%$. Graft failure will be defined as initial myeloid engraftment by day +35, documented to be of donor origin, followed by a drop in the ANC to $<500/\text{mm}^3$ for more than three days, independent of any myelosuppressive drugs, severe GVHD, CMV, or other infection.

Graft rejection will be defined as graft failure with documentation of return of recipient hematopoiesis as determined by cytogenetic and/or chimerism studies.

14.0 STATISTICAL CONSIDERATIONS

Phase I

For the phase I portion of the study, we will employ the modified continual reassessment method (CRM) to determine the maximum tolerated dose (Faries, 1994; Goodman et al., 1995)^{61,62}. Dose-limiting toxicity (DLT) will be as defined under 13.0 and, occurring within the first 21 days after transplant. Dose cohorts of size three will be utilized and we will target the 25th percentile of the tolerance distribution, i.e., the dose level producing DLT in 25% of the patient population. Briefly, the modified-CRM design utilizes a one-parameter, logistic regression model for the dose-toxicity curve

$$p(x) = \frac{\exp(3 + \beta x)}{1 + \exp(3 + \beta x)}, \quad (1)$$

where $p(x)$ is the probability of DLT at dose level x . A prior distribution is assumed for the parameter β and the first three patients are assigned to the lowest dose level. After outcomes are observed for these patients, the posterior distribution for β is calculated and the estimated toxicity probabilities are updated. The next cohort of patients are assigned to the dose level closest to the targeted percentile, with the restriction that doses can not be escalated more than one level at a time. Enrollment is continued until a predetermined total number of patients have been studied, whereupon the MTD is derived based on the final, estimated dose-toxicity curve.

In our trial, the first cohort of three patients will be enrolled at dose level 0 and after all three of these patients have been followed to day 60 the observed number of DLTs will be used to update the posterior distribution and determine the dose level for the succeeding cohort. Since we anticipate an accrual rate of approximately three patients per month, it is likely that all three patients from a given cohort will not have been followed to 60 days before the next eligible patient becomes available. In this case we will assign such patients (termed *excess* patients) to the current dose level; once the original three patients pass the 60-day landmark, we will update the prediction probabilities using all available data. However, so as not to bias the procedure, if *excess* patients have not been followed for a full 60 days, we will not include their toxicity outcomes in the updated analysis, even if a DLT has been observed. A total of 30 patients will be enrolled in the phase I trial.

Because delayed VOD (day 30 and day 60) of moderate severity has been observed in two of the 12 initial patients on study, the observation period for successive patients will be extended to 60 days before dose escalation. This will lead to accrual of a higher number of patients per dose level and therefore we anticipate up to 50 patients in the phase I trial.

Addendum June 2006: Pharmacokinetics for the initial 20 patients was performed in the cancer center core facility at UC. For logistical reasons and for more intensive monitoring another laboratory will be

used and technical modifications in sampling have been introduced. Therefore accrual will resume at dose level 0. This will result in accrual of an additional 20 patients to the protocol.

Phase II

The primary endpoint for the phase II portion of the trial is the disease-free survival rate (DFS) at one year defined as the proportion of patients alive and without evidence of recurrence one year after the initiation of therapy. All patients will be followed for a minimum of one year and we will test the null hypothesis that the DFS rate at twelve months is $\leq 25\%$ versus the alternative that it is at least 40%. A Simon (1989), optimal two-stage design will be employed in which 29 patients are enrolled in the first stage.⁶³ (Patients treated at the MT D during the phase I portion of the study will be included in the phase II trial.) If the number alive and without evidence of recurrence at twelve months is 7 or fewer, the study will be terminated for lack of efficacy. Otherwise, subject to the monitoring described below for graft failure, liver toxicity, and GVHD, an additional 43 patients will be enrolled for a total of 72. If 22 or fewer patients are disease free at 12 months the regimen will be rejected, whereas if 23 or more of the total 72 patients ($> 32\%$) are disease free, the regimen will be considered worthy of further evaluation in phase III trials. This design has an α -level of 10% and a power of 90% under the alternative hypothesis that the true 12-month DFS rate is 40%. The probability of early termination when the 12-month DFS rate is 25% is 0.56. However, to avoid a long suspension of the trial, accrual will continue into the second stage while the one-year outcomes in the 29 first stage patients are being accumulated.

In addition, the incidence of graft failure, liver toxicity, and high-risk, extensive chronic GVHD at 18 months will be closely monitored and evaluated. For the primary endpoint of DFS, we will employ a Simon (1989) two-stage design. Graft failure, liver toxicity, and GVHD will be monitored at specified intervals as described below. An independent Data and Safety Monitoring Committee will be established to review the data and make recommendations regarding the continuation or discontinuation of the trial. This committee is organized by the University of Chicago Cancer Center (High risk protocol monitoring committee). Since the assumptions regarding efficacy and toxicity are the same, the related donor and unrelated donor subgroups will be combined for all analyses.

Adverse Event Monitoring

Graft failure and liver toxicity will be monitored and early termination of the trial will be considered if there is evidence that the graft failure rate is $> 10\%$ or the rate of liver toxicity is $> 15\%$. Specifically, for graft failure the data will be reviewed after successive cohorts of 10 patients have been treated and we will consider terminating the trial if 4 of the first 10, 6 of the first 20, 7 of 30, 9 of 40, 10 of 50, 12 of 60, or 13 of 70 have graft failure. For liver toxicity the trial will be stopped if 5 of the first 10, 7 of the first 20, 9 of 30, 11 of 40, 13 of 50, 15 of 60, or 17 of 70, develop liver toxicity. With regard to high-risk, extensive GVHD, we will review the data after the first 10, 20, and 30 patients with successful engraftment and without evidence of relapse reach their 18-month landmark. (By the time 30 patients have reached this point, all 72 patients will have almost surely been accrued.) Evidence that the rate of high-risk, extensive GVHD is $> 40\%$ will lead to consideration for early stopping. Specifically, if 8 of the first 10, 13 of the first 20, or 17 of 30 such patients develop GVHD at any time

prior to 18 months we will consider terminating the trial. Each of these three stopping guidelines approximates a Pocock (1977)⁶⁴ group sequential monitoring boundary for a one-sided, overall alpha level of 0.10.

Additional Statistical Analyses

At the conclusion of the phase II trial, 90% confidence intervals will be generated for the DFS rate at 12 months, as well as for the incidence of graft failure, and the incidence of active and extensive GVHD. Kaplan-Meier (1958) estimates of disease-free and overall survival rates will be calculated,⁶⁵ and the median disease-free and overall survival times and their associated 90% confidence intervals derived using the method given in Brookmeyer and Crowley (1982).⁶⁶ Descriptive statistics related to the frequency of adverse events, including liver toxicity, and of changes in laboratory values will be generated. Association between GSTA1 enzymatic activity and busulfan metabolic rate (i.e. AUC, T_{1/2}) will be determined using the Pearson correlation coefficient or, in case of a monotone but non-linear relationship, by Spearman's rank correlation coefficient. To account for other determinants of metabolism, multiple linear regression analysis will also be performed. The relationship between enzymatic activity and incidence of VOD will be assessing using logistic regression analysis. Multiple logistic regression analysis may be attempted, depending on the frequency of VOD.

The relationship between GST polymorphisms and VOD will be analyzed using chi-square or Fisher's exact test. The association between polymorphisms and busulfan pharmacokinetics will be analyzed using a t-test or non-parametric Wilcoxon rank-sum test, as appropriate. Finally, the pharmacogenomic determinants of drug efficacy will be assess using Cox (1972) multivariable regression analysis⁶⁷ with time to disease progression or death as the outcome variable and genotype and busulfan pharmacokinetic parameters (AUC, etc.) as predictor variables.

Estimated duration of accrual

For the phase I trial, we estimate approximately 4-5 patients per month will be accrued, so that the target of 30 subjects should be reached in 6-7 months. For the phase II study, we expect to accrue about 30 such patients per year. Assuming about 6-10 patients from the phase I study participate, a little over two years of recruitment and one year of additional follow-up will be required to complete the phase II trial.

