9.1.3 Dose schedule (see also statistical plan)

The targeted daily AUC of busulfan will be determined using the modified continual reassessment method.

Target AUC's are the following:

Dose level 0: 4800 mcgr.min/L.dose

Dose level 1: 5800 mcgr.min/L.dose

Dose level 2: 6800 mcgr.min/L.dose

Dose level 3: 7800 mcgr.min/L.dose

Dose level 4: 8800 mcgr.min/L.dose

Dose level 5: 9800 mcgr.min/L.dose

We do not anticipate further dose-escalation beyond dose level 5. If such dose-escalation were to be considered, we would submit an amended protocol to the IRB.

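### The phase I rule reads the MTD off the final fitted curve without requiring that any patient received that level, so it can name an untested busulfan exposure.

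*Combined protocol and SAP*

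**What the plan says.** Section 9.1.3 lists six target daily AUCs, level 0 (4800) to level 5 (9800), and states: "The targeted daily AUC of busulfan will be determined using the modified continual reassessment method". Anything above level 5 would need an amended protocol.

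Section 14.0, Phase I, uses a one-parameter logistic model with intercept 3, cohorts of three and a 25% DLT target. The next cohort goes to the level closest to target, "with the restriction that doses can not be escalated more than one level at a time". On stopping, it says: "Enrollment is continued until a predetermined total number of patients have been studied", "whereupon the MTD is derived based on the final, estimated dose-toxicity curve".

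Each update waits until the three cohort patients reach day 60. Patients who arrive meanwhile are treated at the current level as excess patients. For those without a full 60 days, "we will not include their toxicity outcomes in the updated analysis, even if a DLT has been observed".

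The total is first given as 30. After the observation period was lengthened, the text says "therefore we anticipate up to 50 patients in the phase I trial". A June 2006 addendum restarts accrual at level 0 with 20 more patients.

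The rest of Section 14.0 presupposes an MTD that patients received. Under Phase II: "Patients treated at the MT D during the phase I portion of the study will be included in the phase II trial". Under Estimated duration of accrual: "Assuming about 6-10 patients from the phase I study participate".

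Appendix A (18.1.1) describes a different method, an up-and-down search for a dose with fewer than 4 DLTs in 12 patients.

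**The concern.** The no-skipping limit governs assignment of the next cohort. The sentence that defines the MTD carries no such limit. Because enrolment stops at a set number and not when the dose has settled, the final curve can differ from the one behind the last assignment, and it can point to a level with no data.

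The MTD is objective 1 and sets the phase II exposure. If an untested level is named, the group of phase I patients treated at the MTD is empty, so the expected 6–10 carry-over patients do not exist. Phase II would then open at least one step higher with no DLT data there. From level 4 to level 5 the step is (9800 − 8800)/8800 = 11% per daily dose. Section 14.0 already reports delayed moderate VOD in 2 of the first 12 patients.

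**Working it through.** The plan gives no operating characteristics for phase I, so there is no stated figure to reproduce. The check has three parts.

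**1. How many patients each update misses.** At 3 per month (Section 14.0) with even arrivals and a 30-day month, one patient arrives every 10 days. The third cohort patient arrives on day 20 and reaches 60 days of follow-up on day 80. Arrivals on days 0, 10, …, 70 make 8 patients on that level (9 if the day-80 arrival is counted there). The update uses 3 of the 8; the other 5 lack 60 days. At the end of enrolment such patients enter only the final curve.

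**2. Worked examples.** Inputs from the plan: p(x) = exp(3 + βx)/[1 + exp(3 + βx)], target 25%. Assumed, because the plan does not state them: an exponential prior on β with mean 1, and x set so that β = 1 returns a prior DLT rate by level of 5/10/17/25/35/45% (coding A) or 10/15/20/25/35/45% (coding B). Hence x = logit(prior rate) − 3; in coding A, levels 3, 4 and 5 have x = −4.099, −3.619 and −3.201. The MTD is the level whose fitted rate is closest to 25%.

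- *8/8/8/8/18 on levels 0–4, DLTs 0/0/1/1/3 (50 patients).* Coding A: posterior mean β = 1.2529. Level 4: 3 − 1.2529 × 3.619 = −1.534, p = 17.7%, distance 7.3 points. Level 5: 3 − 1.2529 × 3.201 = −1.011, p = 26.7%, distance 1.7 points. The rule names level 5, which nobody received. Over both codings, and whether β is plugged in or p is averaged over the posterior, the fitted rates are 16–19% at level 4 and 25–27% at level 5.
- *8/8/8/26 on levels 0–3, DLTs 0/1/1/5 (50 patients).* Coding A: β = 1.0784. Level 3: 3 − 1.0784 × 4.099 = −1.420, p = 19.5%, distance 5.5. Level 4: 3 − 1.0784 × 3.619 = −0.903, p = 28.8%, distance 3.8. The rule names untested level 4, also under coding B.
- *9/9/9/3 on levels 0–3 (30 patients) with no DLT, or one at level 2 or level 3.* Every fitted rate is below 25%, so level 5 is closest. It lies two levels above anything given.

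Over a wider set of 30 settings (five codings, three priors, two estimates), the first example names level 5 in 29 of 30, the second names level 4 in 19 of 30, and the three short cases name level 5 in 90 of 90. The second example therefore depends on the coding.

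**3. Frequency.** The rule was simulated with 50 patients at 3 per month, 60-day updates, excess patients on the current level, no skipping, and all 50 outcomes in the final curve. N = 50 assumes that the 20 added patients replace the first 20. Assumed true DLT rates (%) by level: MTD at level 4, 3/5/8/15/25/40; level 3, 4/8/15/25/40/55; level 2, 8/15/25/40/50/60; level 0, 25/40/50/60/70/75. There were 1500 trials per cell. Ranges cover both codings, both estimates, and even or random arrivals.

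| True MTD | Untested level named | Mean true DLT of level taken forward, affected trials: as written → restricted | All trials taking a level with true DLT ≥ 40%: as written → restricted |
|---|---|---|---|
| Level 4 | 3–20% | 30–37% → 19–23% | 22–44% → 18–35% |
| Level 3 | 2–10% | 33–43% → 20–28% | 23–47% → 21–42% |
| Level 2 | 2–6% | 31–38% → 19–25% | 18–35% → 16–32% |
| Level 0 | under 2% | – | – |

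For a true MTD at level 4, even arrivals give 3–6% and random arrivals 17–20%. Two gamma priors with mean 1 give 5–19%, 3–10%, 2–6% and 1–2% down the first column. A second simulation with other codings and true curves and even arrivals gave 2–10% at N = 50 and 3 per month. The share rises if phase I stops at 30 or accrues at 4–5 per month (the rate under Estimated duration of accrual), but the plan does not clearly pair those inputs with the 60-day hold.

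**The case against.** The strongest reply is that the sentence about the final curve belongs to a brief general description of a cited method, and that the trial's own rules follow it. Those rules, the carry-over of patients treated at the MTD, and even Appendix A's 4-of-12 criterion all presuppose a tested level. Moving phase II to a level nobody received could itself be called an escalation, subject to the one-step limit and the 60-day wait. Phase I has been enlarged before, so the team could simply add a cohort. Phase II also has liver-toxicity and graft-failure boundaries from the first 10 patients and an independent committee.

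Much of this stands. A tested MTD is clearly intended, phase II monitoring limits the harm, and losing 6–10 carry-over patients leaves the Simon test unchanged. The frequencies rest on inputs the plan does not supply, and the upper end for level 4 needs random arrivals. The 9/9/9/3 example uses 30 patients. With 50 at 3 per month and a true MTD at level 2, 3 or 4, naming a level two or more steps above the highest tested occurs in 0% of trials with even arrivals and at most 1.2% with random arrivals. The restriction also still accepts a thinly tested level.

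What does not stand is that the intention closes the gap. The carry-over statements are planning assumptions and give no selection rule. The one-step limit is written for cohort assignment. Appendix A describes a different design that conflicts with Sections 9.1.3 and 14.0.

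**Conclusion.** The concern holds, as a minor point. Read as written, Section 14.0 can name an MTD that no patient received. That conclusion rests on the text and on examples that follow from the stated model under the assumed prior and codings, including two with DLTs observed.

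For 50 patients at 3 per month the simulated share is 2–20% when the true MTD is level 2, 3 or 4, and under 2% at level 0. It depends on the assumed prior, coding, true curves and arrival pattern. In the affected trials the restriction brings the mean true DLT rate of the chosen level from 30–43% down to 19–28%. Over all trials the gain is small, because most choices with a true DLT rate of 40% or more are at levels patients did receive, and this gap does not cause those.

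**What to change.** In Section 14.0, define the MTD as the level with estimated DLT probability closest to 25% among levels given to patients with completed 60-day follow-up. If the curve points above the highest such level, take that highest level into phase II and report that the MTD was not reached. In Appendix A (18.1.1), replace the up-and-down sentence with a reference to Section 14.0.

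The cost is one or two sentences plus one line, and no extra patients. The downside is that when phase I ends while still escalating, a level somewhat below the true MTD may go forward: in the affected trials the mean true DLT rate is 19–23% against the 25% target (true MTD at level 4, 50 patients, 3 per month).

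The sponsor may also require a minimum number at the chosen level, for example 6, the low end of the expected carry-over. That guards against a thinly tested MTD, but in the same setting it raises the chance of reporting the MTD as not reached from 3–20% to 9–36%, so it should remain a choice.
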